18. ADVERSE EVENTS

18.1. ADVERSE EVENT CATEGORIES

For purposes of this protocol the adverse event definitions are derived from GCP standards and FDA Guidance.⁸

Table 4
Adverse Event Definitions

Adverse Event (AE)	Untoward medical occurrence, unintended disease or injury, or untoward clinical signs (including abnormal laboratory findings) in subjects, users or other persons, whether or not related to the medical device. Includes events related to the study device or comparator device, or the procedures involved.
Serious Adverse Event (SAE)	
Adverse event that:
 
▪ Led to death▪ Led to serious deterioration in the health of the subject, that:
○ Resulted in a life-threatening illness or injury, or○ Resulted in a permanent impairment of a body structure or a body function, or○ Required in-patient hospitalization or prolongation of existing hospitalization, or○ Resulted in medical or surgical intervention to prevent life-threatening illness or injury or permanent impairment to a body structure or a body function○ Led to fetal distress, fetal death, or a congenital abnormality or birth defect 
Planned hospitalization for a pre-existing condition without serious deterioration in health, is not considered a serious adverse event. Hospitalization is defined as an admission greater than 24 hours

Adverse Device Effect (ADE)	Untoward and unintended response to a medical device or as a consequence of inadequate labeling and includes any event that is a result of user error.
Serious Adverse Device Effect (SADE)	Untoward medical occurrence that happens in a subject or other person, is related to the study device, comparator, or procedure, and is serious, but is not unanticipated

⁸ Clinical Investigation of Medical Devices for Human Subjects - Part 1: General Requirements. ISO 14155-1. International Organization for Standardization. 2011.

Unanticipated Serious Adverse Device Effect (USADE)	Any serious adverse effect on health or safety or any life-threatening problem or death caused by, or associated with, a device, procedure, or comparator device if that incidence effect, problem, or death was not previously identified in nature, severity, or degree of incidence in the risk analysis report of the plan or application (including a supplementary plan or application), or any other unanticipated serious problem associated with a device that relates to the rights, safety, or welfare of subjects.
---	--

The signs, symptoms, and sequelae of an underlying adverse event (linked pathophysiologically to the AE) should not be reported as separate adverse events.

All adverse events, of any type, are to be recorded on an “Adverse Event Form”. Adverse events are to be characterized by their severity, relatedness the surgical procedure, need for therapy, and resolution status.

Adverse events will initially be characterized as “serious” or “non-serious” by the study investigator.

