15. PROCEDURE PROTOCOL

The device is used in accordance with the instructions for use. An initial target pneumoperitoneal pressure setting of 10mmHg will be used for the procedure. At the discretion of the surgeon investigator, pressure will be adjusted as needed to accomplish the surgical procedure. A standard insufflator with 3mm ports and one 5 mm ports will be used for the procedure.

Table 3
Intraoperative/Procedure Information

Type of Information	Time Point	Data Sources
Date of Procedure	Before opening	Patient Medical Record
Pneumoperitoneum pressure after camera trocar is inserted	Intraoperative	Investigator Report
Increase in pressure and reason for change	Intraoperative	Investigator Report
Adverse Events	Intraoperative	Investigator Report
Unplanned concomitant interventions or procedures	Intraoperative	Investigator Report
End tidal volume of CO ₂ (etCO ₂), recorded at the beginning and end of the procedure.	Intraoperative	Investigator Report
Number of CO ₂ liters consumed	At completion of the procedure	Investigator Report
Surgeon Survey on Quality of Visualization and Smoke Management	Immediately Post-operative	Investigator Report
Ultravision device(s) used (lot# and model #)	Immediately Post-operative	Investigator Report
Diathermy device(s) used	Immediately Post-operative	Investigator Report
Device Malfunction – recorded as an adverse event	Intraoperative	Investigator Report
Number of Endometriosis Lesions Resected	Post-operative	Operative Report / Investigator Report
Pain Assessment	Just Prior to discharge	Medical Record

Table 3
Intraoperative/Procedure Information

Type of Information	Time Point	Data Sources
Pain Medications	Prescribed at discharge	Medical Record

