18.2. ADVERSE EVENT ADJUDICATION

Events are to be initially judged by the investigator as to their relatedness to the study device, surgical procedure, or “other etiology”. The classifications will be “not related”, “probably not related”, “undetermined”, “probably related”, or “related”.

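### Tables 3 and 4 are inconsistent: a serious event due only to the operation is labelled a device effect, and a malfunction that harms no one is recorded as an adverse event

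*Protocol*

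**What the plan says.** Four parts of the protocol bear on how an event is classified.

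- **Table 4, Section 18.1.** An adverse event (AE) is an "Untoward medical occurrence, unintended disease or injury, or untoward clinical signs (including abnormal laboratory findings) in subjects, users or other persons", whatever its relation to the device. An ADE is an "Untoward and unintended response to a medical device or as a consequence of inadequate labeling", and it extends to user error. A SADE is an untoward medical occurrence that "is related to the study device, comparator, or procedure, and is serious, but is not unanticipated". A USADE is a serious, previously unidentified effect "caused by, or associated with, a device, procedure, or comparator device".
- **Text below Table 4, Section 18.1.** All adverse events go on one Adverse Event Form. The attributes listed for each event include its relation to the surgical procedure. Relation to the device is not in that list.
- **Section 18.2.** "Events are to be initially judged by the investigator as to their relatedness to the study device, surgical procedure, or" another etiology, on a five-level scale from not related to related.
- **Table 3, Section 15.** Adverse events have one line. A separate line reads "Device Malfunction – recorded as an adverse event", with no condition that anyone was affected.

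The study is single-arm with 20 patients. Adverse events are named in objective 5 and listed under Other Data Collection. Data are summarised descriptively and read against the manufacturer's other studies and the literature (Section 25.2).

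**The concern.** A serious device effect should be a device effect that is also serious. In Table 4 it is not, because the procedure is admitted at the serious level but not at the parent level. An investigator who follows the table would put a device label on an event that the same investigator has attributed to the surgery alone.

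In the same way, a fault that touches nobody fails Table 4's definition of an adverse event, yet Table 3 has it recorded as one. The generator is battery-operated (Section 4), so a harmless power fault is a realistic example.

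Both rules are applied at the site when the forms are completed, so they are fixed by the protocol and are not a matter for a later analysis plan. At stake is how the safety data under objective 5 read. There is no control arm in which the same labelling would also appear, and Section 5 reports no patient injury reports for the device to date. A single event carrying a serious device-effect label because of the surgery would stand out.

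**Working it through.** The protocol states no event rate or expected count on this point, so there is no figure to reproduce. The check is mainly a comparison of texts.

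**Step 1: relatedness required by each Table 4 category**

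| Category | Device | Procedure alone |
|---|---|---|
| AE, SAE | not required | not required |
| ADE | yes (or labelling, or user error) | not admitted |
| SADE | admitted | admitted |
| USADE | admitted | admitted |

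**Step 2: test case for the device-effect label.** Take a serious, anticipated complication of the laparoscopy that does not arise from the device, its labelling or user error. The investigator rates it under Section 18.2 as not related to the device and related to the surgery.

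- ADE: no.
- SADE: yes, because the limbs are joined by *or* and the procedure limb is met.
- SAE: yes, whatever the SADE wording says.

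So SADE does not nest within ADE. If the event is unanticipated, the USADE row gives the same result.

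**Step 3: test case for malfunction.** Take a generator fault with no effect on the patient, a user or anyone else.

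- Table 4: not an AE, since there is no medical occurrence, disease, injury or sign in a person.
- Table 3: recorded as an AE.

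**Step 4: Section 18.1 against Section 18.2.** Section 18.2 asks for relatedness to the device and to the procedure. The attribute list in Section 18.1 names the procedure only. The two do not agree on whether device relatedness is one of the recorded attributes.

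**Step 5: size if such an event occurs.** With 20 patients as the denominator, one affected patient is 1/20 = 5 percentage points and two are 2/20 = 10 points. For the malfunction limb, the patient-level AE rate moves only if that patient has no other AE; otherwise only the event count moves.

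**Step 6: chance that at least one occurs.** Let p be the per-patient probability of a serious, anticipated, procedure-only complication. The protocol does not give p; the values below are assumptions. With independent patients, P(at least one) = 1 − (1 − p)^20, and the expected number affected is 20p.

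| Assumed p | P(at least one in 20) | Expected number |
|---|---|---|
| 0.5% | 9.5% | 0.1 |
| 1% | 18.2% | 0.2 |
| 2% | 33.2% | 0.4 |
| 5% | 64.2% | 1.0 |
| 10% | 87.8% | 2.0 |

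The same figures apply to a harmless malfunction if p is read as its probability per procedure. A miscount is possible over this range but not certain.

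**The case against.** The strongest reply is that the labels have little effect in this protocol. No ADE, SADE or USADE rate is planned. IRB reporting (Section 18.3) depends on serious adverse events and unanticipated problems, not on the SADE label. AE and SAE definitions ignore relatedness, so the SADE wording changes neither total. No success endpoint uses adverse events, and Section 25.1 says the study is not meant to demonstrate safety and efficacy. All of this stands and limits the importance of the point.

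A second reply is that the raw information survives. Section 18.2 collects device and procedure relatedness, and Table 3 gives malfunction its own line, which may be meant only as a recording route. Device-related serious events and harmless malfunctions could then be separated afterwards. This stands in part. It depends on case report forms that are not shown, and the Section 18.1 attribute list omits the device.

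A reader might infer more than the documents support:

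- **That both counts are bound to be wrong.** An error needs a qualifying event to occur and someone to tabulate by the label.
- **That Table 4 overrides Section 18.2.** Nothing in Table 4 replaces the relatedness judgement; the two simply disagree.
- **That device faults are lost among clinical events.** The separate line in Table 3 speaks against this.
- **That adverse events are the only safety information.** Unplanned concomitant interventions, subsequent surgical interventions and end-tidal CO₂ are also recorded.
- **That the rates could not be compared with those of other studies.** Neither the definitions used in those studies nor the text of the cited standard is in the documents, so this cannot be shown.

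**Conclusion.** The inconsistency is real, and its consequence is limited. Followed literally, the definitions give a device-effect label to a serious event due to the procedure alone, and they record a harmless malfunction as an adverse event. Each affected patient can add 5 percentage points to a descriptive rate, taking 20 as the denominator. Whether this happens depends on event probabilities that the protocol does not state; the chance of at least one such event runs from 9.5% to 87.8% as the assumed probability goes from 0.5% to 10%.

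All-cause SAE totals, IRB reporting of SAEs and the success endpoints are not affected. Only the malfunction rule can inflate the overall AE count. The conclusion rests on the protocol's own definitions. The rewording is worth making because it costs little and the classification is done at the site.

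**What to change.** 1. **SADE:** define it as an ADE that meets a seriousness criterion and is anticipated.
2. **USADE:** limit the device-effect label to device-related events. Unanticipated serious procedure-related events remain captured as SAEs and, where they qualify, as unanticipated problems under Section 18.3, so nothing drops out of reporting.
3. **Section 18.1 attribute list:** add relatedness to the device, so that it agrees with Section 18.2.
4. **Table 3:** record malfunction as a separate device item with patient effect yes or no. Count it as an adverse event only when Table 4's AE definition is met.

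The cost is rewording in Tables 3 and 4 and in Section 18.1, one extra field on the case report form and one extra line of reporting. No visits, patients or procedures are added.

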18.2. ADVERSE EVENT ADJUDICATION

Events are to be initially judged by the investigator as to their relatedness to the study device, surgical procedure, or “other etiology”. The classifications will be “not related”, “probably not related”, “undetermined”, “probably related”, or “related”.

18.3. REPORTING OF ADVERSE EVENTS AND UNANTICIPATED PROBLEMS

Serious adverse events and Unanticipated Problems related to the research will be reported to the Mercy Institutional Review Board.

18.4. SUBSEQUENT SURGICAL INTERVENTIONS

Some complications may lead to a subsequent surgical intervention. The reason for each subsequent surgical intervention and the action taken is recorded on the case report form, along with the identification of the type subsequent surgical interventions accordingly. The exact type of intervention must be specified.

19. PATIENT WITHDRAWAL

A patient may choose to withdraw from participation in the study at any time without penalty. If a patient chooses to withdraw, they will still receive medical care consistent with the standard of care. The investigator may at their discretion withdraw a patient from participation or where intraoperative exclusions (defined in the I/E criteria) occur. Other examples include if the procedure necessitates conversion from laparoscopic to open technique, lack of adherence to visit schedule, adverse events, or safety concerns. For all withdrawals the date, point in the study, and reason for withdrawal will be recorded. Patients that withdraw prior to the procedure or are withdrawn from the study due to an intraoperative exclusion are replaced.

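### Section 19 permits discretionary withdrawal after surgery for adverse events, safety concerns or missed visits and does not provide for scheduled follow-up to continue, so pain and later safety data may be lost selectively

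*Protocol*

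**What the plan says.** Protocol Section 19 gives the power in general terms: "The investigator may at their discretion withdraw a patient from participation". Among its examples are "lack of adherence to visit schedule, adverse events, or safety concerns". It does not limit these to the time before or during surgery.

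On what is documented, it says: "For all withdrawals the date, point in the study, and reason for withdrawal will be recorded". On what the patient receives afterwards, it says: "If a patient chooses to withdraw, they will still receive medical care consistent with the standard of care". That sentence covers only withdrawal by the patient's own choice, and it concerns care, not data. On replacement, it says: "Patients that withdraw prior to the procedure or are withdrawn from the study due to an intraoperative exclusion are replaced". A patient withdrawn after the operation for an adverse event is therefore not replaced.

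Other sections set recording duties with no exception for withdrawn patients:
- Section 18.1: "All adverse events, of any type, are to be recorded on an “Adverse Event Form", and "Adverse events are to be characterized by their severity, relatedness the surgical procedure, need for therapy, and resolution status".
- Section 18.4: "The reason for each subsequent surgical intervention and the action taken is recorded on the case report form".
- Section 17 asks for pain and adverse event assessment at any unscheduled visit.

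The follow-up at issue is in Section 17 and the Study Data Collection Schedule. It consists of a daily pain diary on days 1-7, a clinic visit at 2 weeks (adverse events and a final pain assessment; the schedule adds pain medications), and a 4-week telephone call that collects cosmesis only.

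**The concern.** Stopping an intervention and leaving follow-up are different things, and Section 19 does not separate them. According to the Study Summary and Section 4, the device works only while electrosurgical instruments are in use, so exposure ends with the operation. After that, an adverse event gives no study treatment to discontinue. Section 31 itself says that the study's added assessments bring no new risk. Withdrawal at that stage can therefore only take away observations.

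Two of the grounds, adverse events and safety concerns, are themselves outcomes. If they lead to withdrawal, missingness depends on how the patient fared. Post-surgery pain and pain medication use are endpoints 4 and 5, on which the Study Summary says success will be based. The study has one arm and its results are read against outside studies and literature (Section 25.2), so no concurrent control would share the loss. The investigator who holds this discretion also rates visualization (Section 16), makes the initial judgement of adverse event relatedness (Section 18.2) and is responsible for analysis and reporting (Section 27).

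**Working it through.** The protocol gives no withdrawal rate, expected pain score or standard deviation, so there is no figure of its own to reproduce. The check has two parts.

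**1. What is still captured after a postoperative withdrawal for an adverse event**

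| Item | Source | Secured after withdrawal? |
|---|---|---|
| Date, point in study, reason | Section 19 | Yes |
| The triggering adverse event | Section 18.1 | Yes, no exception stated |
| Re-operation | Section 18.4 | Required, no exception stated |
| Assessment at an unscheduled visit | Section 17 | Not stated whether withdrawn patients are covered |
| Remaining diary days | Section 17 | Not provided for |
| 2-week adverse event and final pain assessment | Section 17, schedule | Not provided for |
| 4-week cosmesis call | Section 17, schedule | Not provided for |

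The schedule marks adverse events at the preoperative, procedure, discharge, 2-week and unscheduled contacts. It does not mark them for the diary or the 4-week call. The 2-week visit is thus the one scheduled adverse event inquiry after discharge. A patient withdrawn at the end of day 2 would, if follow-up ended there, miss that visit and 5 of 7 diary days (5/7 = 71%).

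**2. Illustration of size (assumed inputs except N = 20, from Section 7)**

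Let k patients be lost, with mean pain d NRS points above the rest. The full mean exceeds the mean of those remaining by k × d / 20.
- d = 4: k = 1 gives 4/20 = 0.2; k = 2 gives 8/20 = 0.4; k = 3 gives 12/20 = 0.6.
- Over d = 2 to 6 and k = 1 to 3, the range is 2/20 = 0.1 to 18/20 = 0.9.

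This applies in full to an assessment that the lost patients miss altogether, such as the final pain score. It is an upper figure for the diary, because scores given before withdrawal exist. Suppose all diary days are pooled (20 × 7 = 140 patient-days), d = 4 on every day, and days 1-2 are kept:
- k = 1: 28/140 − 8/135 = 0.20 − 0.06 = 0.14
- k = 2: 56/140 − 16/130 = 0.40 − 0.12 = 0.28
- k = 3: 84/140 − 24/125 = 0.60 − 0.19 = 0.41

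With no assumption about the missing scores on the 0-10 scale, the mean of a missed assessment is undetermined over a width of 10k/20, which is 0.5, 1.0 or 1.5 points for k = 1, 2, 3.

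The chance of at least one such withdrawal among 20 is 1 − (1 − p)^20. For assumed p of 2%, 5% and 10%, this is 33%, 64% and 88%.

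**The case against.** The strongest reply is that the protocol captures more than Section 19 suggests, and that nothing in it ends follow-up. Much of this stands:

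- A reader might infer that only date, point and reason are ever recorded. That is true of Section 19 but not of the protocol, because Sections 18.1 and 18.4 require the adverse event form and the re-operation record without exempting withdrawn patients.
- A reader might infer that follow-up stops in the patients who were harmed. No section says so; it is a reading of withdrawal from participation combined with silence. Withdrawal is also discretionary, so not every patient with a complication is affected. The 2-week visit is standard of care and would probably take place anyway, and resolution status might be read from the medical record.
- A reader might infer that the analysis denominator shrinks. Not being replaced is not the same as being excluded. Analysis sets may be defined in an SAP that is not shown.
- The study is a small post-market feasibility study with descriptive analysis and no pain threshold, so no stated decision turns on a few tenths of an NRS point. Pressure and visualization are recorded during or just after surgery and are unaffected by later withdrawal.

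These points limit the finding but do not supply the missing provision. A standard-care visit yields study data only if someone is still charged with collecting them. The unscheduled-visit rule does not say that it reaches withdrawn patients. An SAP can define how missing data are handled but cannot recover diary entries or inquiries that were never made.

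**Conclusion.** The concern holds in a limited form. Section 19 permits withdrawal for reasons tied to outcome at a time when no study treatment remains to be stopped, and it leaves open whether the scheduled diary, 2-week and 4-week assessments continue. Selective loss is therefore possible, not certain. The likely direction is favourable to the study: lower reported pain and pain medication use, and fewer later safety findings.

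The size cannot be obtained from the protocol. The 0.2 to 0.6 NRS points rest on two assumptions, 1 to 3 patients lost and pain 4 points higher in them. They are upper figures where early diary scores are kept. Each patient is 1/20 = 5% of the sample. The point should be corrected because the remedy is cheap. It does not undermine the intraoperative endpoints.

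**What to change.** Add to Section 19 that, once use of the device has been attempted:

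1. Adverse events, safety concerns and missed visits are not grounds for ending data collection.
2. These patients stay in the scheduled diary, the 2-week adverse event and pain assessment and the 4-week cosmesis call, unless they withdraw consent.
3. Adverse events are followed to resolution or the last scheduled contact.
4. All data collected stay in the analysis, and these patients stay in the safety denominator.

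This concerns data collection only and leaves clinical decisions with the investigator. For missed visits it cannot recover an assessment that the patient did not attend, but it keeps the remaining contacts open. The existing rule on replacing patients can stand.

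The cost is a few sentences. The 2-week visit is already standard of care and the call is already scheduled. The downside is that reported adverse event and pain results may look slightly less favourable.
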